**Figure 2: StepWatch****Figure 3: StepWatch data output**

(birresearch), accessible only by authorized study staff. No data will be stored in temporary files or on hard drives.

Randomization

Participants will be assigned to MP or UC using cluster randomization based on hospital ward at both the Birmingham VAMC and UAB Hospital. At study initiation, all five wards at the Birmingham VAMC will be assigned to the usual care group. Every 5 months a randomly chosen ward will shift from receipt of usual care to the mobility program (See Figure 4). At UAB Hospital, all four wards will be assigned to the usual care group at study initiation, which is expected to be at month 24 of the study. Every 3 months a randomly chosen study ward will shift from receipt of usual care to the mobility program (See Figure 4A). MP patients will receive three daily visits for progressive ambulation; the UC group will receive three daily “friendly visits.” Both groups will receive routine medical care as it is currently provided, including the provision of physical therapy if ordered by the physician.

Figure 4: Stepped Wedge Cluster Randomization with 5 VA Hospital Units. The order in which each unit receives the intervention is randomized, with staggered implementation. By conclusion of observation, all units have received the intervention. MP (grey bars) = Mobility Program initiated and continued on ward unit.

	Time (in months)						
Unit	1/18/17- 6/18/17	6/19/17 – 11/18/17	11/19/17 – 4/18/18	4/19/18 – 9/18/18	9/19/18 – 2/18/19	2/19/19 – 7/18/19	7/19/19 – 12/31/19
A	Control	MP					
B	Control		MP				
C	Control			MP			
D	Control				MP		
E	Control					MP	

Figure 4A: Stepped Wedge Cluster Randomization with 4 Hospital Units at UAB Hospital. The order in which each unit receives the intervention is randomized, with staggered implementation. By conclusion of observation, all units have received the intervention. MP (grey bars) = Mobility Program initiated and continued on ward unit.

	Time (in months)					
Unit	5/1/18 – 7/31/18	8/1/18 – 10/31/18	11/1/18 – 1/31/19	2/1/29 – 4/30/19	5/1/19 – 7/31/19	8/1/19 – 12/31/19
A	Control	MP				
B	Control		MP			
C	Control			MP		
D	Control				MP	

Daily visits

Mobility Program Group (MP):

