Condensed Memorial Symptom Assessment Scale (CMSAS)	5 minutes	Once
Gait speed	5 minutes	Once
Chart review	0 minutes (performed by staff)	Once
Total	13 minutes	

Post-Discharge Follow-ups

After discharge, participants will be contacted monthly for the first 6 months, at month 9, and at month 12 for follow-up assessments. These assessments will occur over the phone, except in the unlikely event that the participant is hospitalized at BVAMC or UAB Hospital during the assessment window; in that case, the follow-up may occur in the participant's hospital room. Study staff will attempt to contact participants for up to one week after the initiation of the calls. If patients have not been reached within five days of their scheduled call date, the designated contacts provided by the participant will be contacted to help determine if the participant is out of town, hospitalized, admitted to a nursing home, or has died. If the participant cannot be reached within one week

of the initiation of the follow-up call, that follow-up call will be marked as missing and no further calls will be attempted until the next scheduled follow-up. The participant's EMR will also be reviewed by study staff for outcomes of interest including rehabilitation services, ED visits, hospitalizations and discharge diagnoses, nursing home placement, hospice services, and death.

As at baseline, the depression screening tool PHQ – 2 will be administered during each post-discharge follow-up to the participant (surrogate responses will not be solicited). If a participant is noted to have a PHQ-9 ≥ 11 , indicating moderate depression, the participant's VA or UAB primary care physician will be notified by study staff, provided the participant isn't already on an antidepressant or is being followed by mental health.

If a participant successfully completes a follow-up assessment, a letter will be mailed thanking them for their continued participation and reminding them of the next follow-up assessment; when the final follow-up is completed, a letter will be sent thanking them for their contribution and stating that their participation has now ended. If a participant cannot be successfully contacted for a follow-up, a letter will be sent asking them to please contact study staff so that either their contact information can be updated, or so that they may withdraw from the study.

TABLE 7

Post-Discharge Assessments: Months 1, 2, 4, & 5

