regularly meet by phone (e.g., Nurse Executives). Finally, we will seek out opportunities to present our findings to frontline staff (e.g., through quality collaboratives or other activities coordinated through the National Center for Patient Safety).

Limitations of the Study: Maintenance of blinding is a potential limitation. It is possible the Assessor will observe the veteran walking, or will be told information about the group assignment by the patient or healthcare provider. We will address this concern in three ways. First, we will regularly encourage the participant not to share their group assignment with the Assessor. In addition, we will provide **all** patients with identical StepWatches®. Lastly, after the patient completes the study, we will ask the Assessor to identify which group they believe the patient was assigned. There is a risk that the walking intervention will lead to adverse outcomes, such as an increase in falls. Our previous pilot study of a mobility intervention demonstrated the intervention group experienced no falls while three falls occurred among patients in the control group. However, despite these positive results, we will make every effort to provide a safe environment for the increased mobility we are proposing by encouraging patients to both recognize and not exceed their mobility capabilities, and by emphasizing that help is readily available and should be requested if needed. We will also provide ambulatory devices to persons who request them and demonstrate safe use. The selection of a Data Safety and Monitoring Board will be critical to help us achieve this objective of the study, i.e. being falls and injury free. (See Human Studies Section for details).

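### The SAP's assessor-blinding measures leave the ward-and-date route to the arm open, and its planned group guess cannot be judged against 50%

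*SAP*

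**What the plan says.** The SAP, under Limitations of the Study, calls maintenance of blinding a potential limitation. It recognises two ways it could fail: the Assessor sees the patient walking, or the patient or a provider reveals the group. Three measures follow. The first is "First, we will regularly encourage the participant not to share their group assignment with the Assessor". The second is identical StepWatches for everyone. The third is that "after the patient completes the study, we will ask the Assessor to identify which group they believe the patient was assigned".

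The Protocol (section E, Randomization) fixes how the arm arises: "Participants will be assigned to MP or UC using cluster randomization based on hospital ward at both the Birmingham VAMC and UAB Hospital". At the VA, "At study initiation, all five wards at the Birmingham VAMC will be assigned to the usual care group", and then "Every 5 months a randomly chosen ward will shift from receipt of usual care to the mobility program". UAB also starts with all wards in usual care, and there "Every 3 months a randomly chosen study ward will shift from receipt of usual care to the mobility program". The captions of Figures 4 and 4A add: "By conclusion of observation, all units have received the intervention". The Analytic Approach analyses each patient by the unit's condition at admission, and the recruitment section has participants told that their ward decides their group.

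The LSA is the primary outcome. Study staff collect it in hospital at baseline and then at eight follow-up contacts, normally by telephone: "Study staff will attempt to contact participants for up to one week after the initiation of the calls". Study staff also review the medical record, and Tables 7 to 9 list chart review beside the LSA at every contact. The Protocol mentions neither outcome-assessor blinding nor an Assessor role.

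**The concern.** The three measures would suit a trial that randomises individual patients, where the arm stays unknown unless someone leaks it. Here the arm can be worked out without a leak by anyone holding the ward, the admission date and the switch schedule. None of the measures hides those items. The third does not protect blinding at all. It checks it afterwards, once every LSA for that patient has been recorded, so the answer may reflect the outcomes observed.

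The LSA and the two secondary mobility outcomes (driving and walking a quarter mile) are interview answers. If an interviewer who knows the arm probes or scores differently by arm, that lean moves with the intervention indicator, whose significance is the primary test. Secular-trend terms and multiple imputation cannot separate the two.

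**Working it through.** The plan gives no figure for blinding, so there is none to reproduce. The check codes the schedules in Figures 4 and 4A.

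**Inputs.** Period dates and switch order come from Figures 4 and 4A; the 2/1/29 entry in Figure 4A is read as 2/1/19. Accrual is assumed even over wards and days within each hospital.

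**Step 1: ward plus date.** Each ward-by-period cell holds one condition: 5 × 7 = 35 of 35 cells at the VA and 4 × 6 = 24 of 24 at UAB. Ward, date and schedule together fix the arm.

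**Step 2: hospital and date, ward hidden.** With p the share of wards in the mobility program on a given date, the best guess is right with probability max(p, 1 − p). This presumes knowledge of how many wards have switched, but not which ones.

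| Hospital | Period | Days | Wards in MP | Best guess right |
|---|---|---|---|---|
| VA | 1 | 152 | 0/5 | 1.00 |
| VA | 2 | 153 | 1/5 | 0.80 |
| VA | 3 | 151 | 2/5 | 0.60 |
| VA | 4 | 153 | 3/5 | 0.60 |
| VA | 5 | 153 | 4/5 | 0.80 |
| VA | 6–7 | 150 + 166 | 5/5 | 1.00 |
| UAB | 1 | 92 | 0/4 | 1.00 |
| UAB | 2 | 92 | 1/4 | 0.75 |
| UAB | 3 | 92 | 2/4 | 0.50 |
| UAB | 4 | 89 | 3/4 | 0.75 |
| UAB | 5–6 | 92 + 153 | 4/4 | 1.00 |

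- Date alone fixes the arm: VA 152 + 150 + 166 = 468 of 1,078 days (43%); UAB 92 + 92 + 153 = 337 of 610 days (55%).
- Mixed periods, VA: (153×0.8 + 151×0.6 + 153×0.6 + 153×0.8)/610 = 427.2/610 = 0.70.
- Mixed periods, UAB: (92×0.75 + 92×0.5 + 89×0.75)/273 = 181.75/273 = 0.67.
- Overall: VA (468 + 427.2)/1,078 = 0.83; UAB (337 + 181.75)/610 = 0.85.

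So 50% is the wrong reference for the planned guess. Always answering mobility program would be right for 57.6% (VA) and 62.4% (UAB), the program's share of ward-time.

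**Step 3: illustration of bias.** The documents give neither an interviewer lean nor a standard error (SE), so both are assumed. Two-sided error with lean b is Φ(−1.96 + b/SE) + Φ(−1.96 − b/SE). Taking exactly 90% power at 10 points gives SE = 10/(1.960 + 1.282) = 3.085; the plan says more than 90%. An SE of 5 is a second assumption.

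| Assumed lean (LSA points) | SE 3.085 | SE 5 |
|---|---|---|
| 1 | 6.2% | 5.5% |
| 2 | 9.9% | 6.9% |
| 3 | 16.3% | 9.2% |

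The calculation applies the full lean throughout, as if every caller knew the arm and leaned equally.

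**The case against.** The strongest reply is that nothing shows the telephone caller holds the ward or the schedule. Calls are made from private offices after discharge. The SAP names a distinct Assessor who might happen to see a walk, which suggests someone who does not deliver walks. The SAP also refers to figures and sections not included in it, so a role definition may exist elsewhere. This stands in part. A reader might infer that callers knew the arm for every patient, but the documents do not say so; they are silent on what callers could see. The silence still matters. Calls for the VA are placed from the same offices that hold its hard-copy study records, and generic study staff make calls, deliver sessions and review charts.

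The SAP already lists blinding as a limitation, so a reader who infers that it claims secure blinding, or that no masking is possible here, goes too far. What is missing is the main route to the arm.

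Participants know what they received, so masking callers leaves their own reporting bias in place. The friendly visits partly balance attention and expectation, but do not affect what the interviewer knows. Both points limit the gain without removing it.

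An early guess still follows one LSA, misses later unblinding and might prime the caller for the seven remaining contacts. It is less coloured by outcomes than a guess after all eight, but it is not clean.

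Lastly, the Protocol is dated February 2021 and the figures end enrolment on 12/31/19. On that schedule, changes to call procedures may come too late.

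**Conclusion.** The gap is real and cheap to narrow. The stated measures miss the ward-and-date route, and neither document withholds ward, date or schedule from LSA assessors or separates their role. With ward hidden, guess accuracy in mixed periods would be 70% (VA) and 67% (UAB), against certainty for someone holding ward, date and schedule. Overall it would still be 83% and 85%. These figures rest on the published dates, even accrual and knowledge of how many wards have switched.

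A reader might also infer a type I error as high as 16.3%. The documents do not support that as an estimate: the lean is assumed, the SE is back-solved, and an assumed SE of 5 gives 5.5% to 9.2% over the same leans. Nor should the point be stretched to treat ADL, IADL or falls as secondary hypotheses. The plan names driving and the quarter-mile walk; it analyses ADL and IADL as adverse outcomes and gives falls no analysis under Aim 1.

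**What to change.** 1. Remove index ward, arm and switch schedule from the follow-up call sheet and the database view used for calls. The due date remains and still hints at the admission date, so masking is partial.
2. Where existing staffing allows, have calls made by staff who did not deliver that participant's visits. Do the chart review after the LSA interview, or give it to someone else, because the chart may show the ward.
3. Record the Assessor's guess and its reason early, for example after the month-1 LSA. Report it by arm and by mixed versus single-arm period, against the date-only benchmark and not 50%.
4. Amend the SAP's Limitations of the Study to define the Assessor, name the ward-and-date route and say that masking is partial. Report the LSA results accordingly.

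For calls already completed, document who made them and what they could see, then apply item 4 and the date-only benchmark to whatever guesses exist.

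The cost is a restricted call sheet, a rota rule, one question moved and some wording, with some scheduling inconvenience and an open admission that masking is partial. Randomisation, sample size and the analysis model are unchanged. Participants' own reporting bias is not removed.
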